## 3.4 EXPLORATORY ENDPOINTS ANALYSIS

The exploratory endpoints described in this section are the change from baseline to Week 24 efficacy endpoints and PGIC at Week 24. Other exploratory endpoints analyses are defined in [Section 3.7.1.3](#) (biomarkers) and [Section 3.7.1.4](#) (health care resource utilization and productivity). Analyses of [REDACTED] in the type-2 inflammation transcriptome signature, as well as endpoints related to [REDACTED] will be addressed in separate documents.

### 3.4.1 Definition of endpoints

EQ-5D-5L health status will be converted into a single index value by using value sets based on UK population. The anterior/posterior rhinorrhea score is the average of the anterior and posterior scores. The ACQ-6 global score is the mean of the 6 questions. UPSIT score and the SNOT-22 total score are the sum of all items.

For endpoints related to sinonasal symptom diary (NC, anterior/posterior rhinorrhea, facial pain/pressure, loss of smell and headache), the 28-day average scores will be used for analysis ([Table 8](#)).

For the three-dimensional CT volumetric measurement of the paranasal sinuses, each test (air volume, lateral wall thickness, volume occupied by disease, and mucosal volume), including location (ethmoid sinus, frontal sinus, maxillary sinus, and sphenoid sinus), laterality (right and left) and direction (anterior and posterior for ethmoid sinus) will be analyzed separately and as the mean of the left and right measurements. The total volume occupied by disease in all sinuses will also be summarized.

### 3.4.2 Main analytical approach

Change from baseline to Week 24 endpoints and PGIC at Week 24 will be analyzed on the ITT with screening blood eosinophil count  $\geq 300$  cells/mm^3 population comparing dupilumab to placebo except for the following:

- Change from baseline to Week 24 in FEV1 and in ACQ-6 will be analyzed on the ITT with screening blood eosinophil count  $\geq 300$  cells/mm^3 and with comorbid asthma subgroup in the dupilumab group.
- Change from baseline to Week 24 in LMK and in sTSS will be analyzed on the ITT population (regardless of blood eosinophil count) in the dupilumab group.

Handling of IEs will follow that of the primary endpoint. Otherwise, no missing data will be imputed. Descriptive statistics will be provided by intervention group. For endpoints comparing dupilumab to placebo, treatment difference (dupilumab vs placebo) and the corresponding 95% CI will be provided. For endpoints analyzed in the dupilumab group, 95% CI in the dupilumab group will be provided. The 95% CI will be constructed based on the t distribution.

### 3.4.3 Exploratory analyses on the [REDACTED] [REDACTED]

Change from baseline to Week 24 in [REDACTED] comparing dupilumab to placebo will be analyzed using the same approach as the secondary endpoints on the [REDACTED] populations.

## 3.5 MULTIPLICITY ISSUES

No adjustments for multiplicity are planned for this Phase 2 study.

## 3.6 SAFETY ANALYSES

All safety analyses will be performed on the safety population as defined in [Section 2](#), unless otherwise specified, using the following common rules:

- The analysis of the safety variables will be essentially descriptive, and no testing is planned.
- Safety data in participants who do not belong to the safety population (eg, exposed but not randomized) will be provided.

### 3.6.1 Extent of exposure

The extent of IMP exposure will be assessed by the duration of IMP exposure and compliance and summarized within the safety population.

## Duration of IMP exposure

Duration of IMP exposure is defined as last IMP administration date – first IMP administration date + 14 days, regardless of unplanned intermittent discontinuations. If the date of the last dose of IMP is missing, the duration of IMP will be left as missing.

Duration of IMP exposure will be summarized quantitatively and categorically: >0 and  $\leq$  2 weeks, >2 and  $\leq$  4 weeks, >4 and  $\leq$  8 weeks, >8 and  $\leq$  12 weeks, >12 and  $\leq$  16 weeks, >16 and  $\leq$  20 weeks, >20 and  $\leq$  24 weeks, >24 and  $\leq$  28 weeks, >28 and  $\leq$  32 weeks, >32 and  $\leq$  36 weeks, >36 and  $\leq$  40 weeks, >40 and  $\leq$  44 weeks, >44 and  $\leq$  48 weeks, >48 and  $\leq$  52 weeks, >52 weeks and  $\leq$  52 weeks + 3 days, >52 weeks + 3 days.

Additionally, the cumulative duration of treatment exposure (expressed in participant-years) will be provided.

## Treatment compliance

A given administration will be considered noncompliant if the participant did not take the planned dose as required by the protocol. No imputation will be made for participants with missing or incomplete data.

Percentage of treatment compliance for a participant will be defined as the number of administrations that the participant was compliant divided by the total number of administrations that the participant was planned to take from the first administration of IMP up to the actual last administration of IMP.

Treatment compliance will be summarized quantitatively and categorically: <80%,  $\geq$  80%.

### 3.6.2 Adverse events

#### General common rules for adverse events

All adverse events (AEs) will be coded to a lower-level term (LLT), preferred term (PT), high-level term (HLT), high-level group term (HLGT), and associated primary system organ class (SOC) using the Medical Dictionary for Regulatory Activities (MedDRA) version currently in effect at Sanofi at the time of database lock.

The AEs will be analyzed in the following 3 categories:

- Pre-treatment AEs: AEs that developed, worsened or became serious during the pre-treatment period.
- Treatment-emergent adverse events (TEAE)s: AEs that developed, worsened or became serious during the treatment-emergent period
- Post-treatment AEs: AEs that developed, worsened or became serious during the post-treatment period

Similarly, deaths will be analyzed in the pre-treatment, treatment-emergent and post-treatment periods.

The primary AE analyses will be on TEAEs. Pre-treatment and post-treatment AEs will be described separately.

An AE with incomplete or missing date/time of onset (occurrence, worsening, or becoming serious) will be classified as a TEAE unless there is definitive information to determine it is a pre-treatment or a post-treatment AE.

If the assessment of the relationship to IMP is missing for an AE, this AE will be assumed as related to IMP. Missing severity will be left as missing.

Multiple occurrences of the same event in the same participant will be counted only once in the tables within a treatment phase.

The AE tables will be sorted as indicated in [Table 4](#).

**Table 4 - Sorting of AE tables**

AE presentation	Sorting rules
SOC, HLGT, HLT and PT	By the internationally agreed SOC order and by alphabetic order of HLGTs, HLTs and PTs.
SOC and PT	By the internationally agreed SOC order and decreasing frequency of PTs a
SMQ/CMQ and PT	By decreasing frequency of SMQs/CMQs and PTs a
PT	By decreasing frequency of PTs a

a Sorting will be based on the dupilumab 300mg q2w group

### **Analysis of all adverse events**

The overview of TEAE with the details below will be generated:

- Any TEAE
- Any severe TEAE
- Any treatment-emergent SAE
- TEAE leading to death
- Any TEAE leading to permanent study intervention discontinuation
- Any treatment-emergent AESI
- Any treatment-emergent other AE of interest grouping
- Any TEAE related to IMP

The AE summaries of [Table 5](#) will be generated with number (%) of participants experiencing at least one event.

**Table 5 - Analyses of adverse events**

Type of AE	MedDRA levels
All TEAE	Primary SOC, HLGT, HLT and PT
	Primary SOC and PT
	PT
	Primary and secondary SOC, HLGT, HLT and PT
Common TEAE ( $\geq 5\%$ in any group)	Primary SOC and PT
TEAE related to IMP as per Investigator's judgment	Primary SOC and PT
TEAE by maximal intensity	Primary SOC and PT
Treatment-emergent SAE	Primary SOC and PT
Treatment emergent SAE related to IMP as per Investigator's judgment	Primary SOC and PT
TEAE leading to permanent intervention discontinuation	Primary SOC and PT
TEAE leading to death b	Primary SOC and PT
COVID-19 related TEAE	Primary SOC and PT
Pre-treatment AE	Overview a
Post-treatment AE	Overview a

a Will include the following AE categories: any AEs, any serious AEs, any AEs leading to death, any AEs leading to permanent intervention discontinuation (pre-treatment AEs only)

b Death as an outcome of the AE as reported by the Investigator in the AE page

### **Analysis of deaths**

In addition to the analyses of deaths included in [Table 5](#) the number (%) of participants in the following categories will be provided:

- Deaths during the treatment-emergent and post-treatment periods
- Deaths in non-randomized or randomized but not treated participants

### **Analysis of adverse events of special interest (AESIs) and other AEs of interest**

Adverse events of special interest (AESIs) and other AEs of interest will be selected for analyses as indicated in [Table 6](#). Number (%) of participants experiencing at least one event will be provided for each event of interest, by PT if applicable. Tables will be sorted as indicated in [Table 4](#).

**Table 6 - Selections for AESIs and other AEs of interest**

AESIs and other AEs of interest	Criteria
AESI	
Anaphylactic reaction	Anaphylactic reaction algorithmic approach (Introductory Guide for Standardised MedDRA Queries (SMQs) Version 18.1): includes anaphylactic reaction narrow SMQ (20000021) terms and programmatic identification of cases based on occurrence of at least two preferred terms meeting the algorithm criteria occurring within 24 hours of each other. The latter cases identified using the algorithm will undergo blinded medical review taking into account the timing of events relative to each other and to IMP administration for final determination of an anaphylactic reaction or not.
Systemic hypersensitivity reactions	SMQ [20000214] hypersensitivity narrow search and [AE corrective treatment/therapy = 'Y' or Action taken with IMP = 'Drug withdrawn' or Action taken with IMP = 'Drug interrupted'] followed by blinded medical review (documented process) for selection of relevant systemic hypersensitivity events
Helminthic infections	CMQ10544 based on HLGT as "Helminthic disorder"
Any severe type of conjunctivitis	CMQ10498 based on PTs (See Section 5.5 a ) and "Severe" ticked in Adverse Events eCRF page
Any severe type of blepharitis	CMQ10497 based on HLTT as "Lid, lash and lacrimal infections, irritations and inflammations" and "Severe" ticked in Adverse Events eCRF page
Keratitis	CMQ10642 based on the following PTs [keratitis, allergic keratitis, ulcerative keratitis, atopic keratoconjunctivitis, herpes ophthalmic, ophthalmic herpes simplex, corneal infection] a
Clinically symptomatic eosinophilia (or eosinophilia associated with clinical symptoms) b	CMQ10641 based on HLTT = Eosinophilic disorders or PT = Eosinophil count increased followed by blinded medical review
Pregnancy of female participants entered in a study as well as pregnancy occurring in a female partner of a male participant entered in a study with IMP	"Pregnancy" or "Partner Pregnancy" checked on the Pregnancy eCRF page as reported by the investigator
Significant ALT elevation	"ALT increase" and AESI answer "Yes" checked on AE eCRF as reported by the Investigator (ALT >5 x ULN in participants with baseline ALT ≤2 x ULN; OR ALT >8 x ULN if baseline ALT >2 x ULN)
Symptomatic overdose with IMP	Symptomatic Overdose is answered Yes, with Overdose of Study Treatment answered Yes on AE eCRF.
Symptomatic overdose with NIMP	Symptomatic Overdose is answered Yes, with Overdose of NIMP answered Yes on AE eCRF.
Other selected AE Grouping	
Serious injection site reactions or severe injection site reactions that last longer than 24 hours	HLTT = 'Injection site reactions' and either with serious status, or with severe status and (AE end date/time - AE start date/time) ≥24 hours or ongoing
Severe or serious infection	Primary SOC = 'Infections and infestations' and with severe or serious status
Parasitic infection	Infection type "Parasitic" checked on eCRF "Infection Event Form"
Opportunistic infection	Has the AE been assessed as opportunistic infection? is answered Yes on eCRF "Infection Event Form"

AESIs and other AEs of interest	Criteria
Drug-related hepatic disorder	SMQ [20000006] Drug-related hepatic disorders- narrow
Injection site reactions	HLT = 'Injection site reactions'
Malignancy	SMQ [20000091]- Malignant or unspecified tumors narrow
Conjunctivitis (narrow)	CMQ10644 based on the following PTs [Conjunctivitis, Conjunctivitis allergic, Conjunctivitis bacterial, Conjunctivitis viral, Atopic keratoconjunctivitis] a
Conjunctivitis (broad)	CMQ10645 based on the following PTs [Conjunctivitis, Conjunctivitis allergic, Conjunctivitis bacterial, Conjunctivitis viral, Atopic keratoconjunctivitis, Blepharitis, Dry eye, Eye irritation, Eye pruritus, Lacrimation increased, Eye discharge, Foreign body sensation in eyes, Photophobia, Xerophthalmia, Ocular hyperaemia, Conjunctival hyperaemia] a
Conjunctivitis █ c	CMQ10643 based on the following PTs [Conjunctivitis, Conjunctivitis allergic, Conjunctivitis bacterial, Conjunctivitis viral, Eye irritation, Eye inflammation, Giant papillary conjunctivitis] a
Keratitis █ c	CMQ30102 based on the following PTs [keratitis, allergic keratitis, ulcerative keratitis, atopic keratoconjunctivitis, ophthalmic herpes simplex] a

a The list of terms may be adjusted according to MedDRA version changes

b All cases of Eosinophilia will be included in the analysis, where cases associated with clinical symptoms will be further described in the CSR

c Labeling subgroup of preferred terms included in the USPI for Dupixent.

The following summaries will be provided:

- All TEAEs, by selected standardized MedDRA query (SMQ)/Customized MedDRA query (CMQ) and PT, showing the number (%) of participants with at least 1 PT.
- For each AESI and other selected AE groupings,
  - Number (%) of participants with any TEAE
  - Number (%) of participants with any serious AE (regardless of treatment-emergent status)
  - Number (%) of participants with any treatment-emergent serious AE
  - Number (%) of participants with any AE leading to death
  - Number (%) of participants with any TEAE leading to permanent study intervention discontinuation
  - Number (%) of participants with any TEAE related to IMP reported by investigator
  - Number (%) of participants with any TEAE by maximum intensity, corrective treatment, and final outcome
  - Number (%) of participants with any TEAE adjusted by the exposure duration
- Number (%) of participants with injection site reactions by the related injection.
- Number (%) of participants with different number of injection site reactions.

In addition, AESIs reported by the investigator in eCRF will be summarized separately.

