Systemic hypersensitivity is established as an important identified risk with dupilumab. As protein therapeutics, all monoclonal antibodies are potentially immunogenic. Rare serious and systemic hypersensitivity reactions have been observed in the dupilumab program including serum sickness/serum sickness-like reaction in the adult AD program and anaphylaxis related to dupilumab in the adult asthma clinical trials.

The important potential risk for dupilumab is "eosinophilia associated with clinical symptoms in asthma patients." The observed increase in eosinophil count is transient, which is consistent with the current understanding of the mechanism of action of dupilumab. In dupilumab asthma studies, a small number of patients with asthma experienced serious systemic eosinophilia presenting with clinical features of eosinophilic pneumonia or vasculitis consistent with eosinophilic granulomatosis with polyangiitis, conditions which are often treated with systemic corticosteroid therapy. These events have been seen in other drug development programs for severe asthma and usually, but not always, have been associated with the reduction of oral corticosteroid therapy suggesting possible unmasking of these conditions with tapering of corticosteroids during dupilumab therapy. The association of dupilumab treatment and these events has not been established. Health care providers should be alert to eosinophilia associated with vasculitic rash, worsening of pulmonary symptoms, pulmonary infiltrate, cardiac complications, and/or neuropathy presenting in their patients, especially upon reduction of SCS.

Patients with known helminth infections were excluded from participation in clinical studies; therefore, it is not known if dupilumab will influence the immune response against helminth infections. Consequently, patients with pre-existing helminth infections should be treated for their helminth infection before initiating therapy with dupilumab.

The common ADR across all indications is injection site reactions. Other potential risks based on the safety profile in particular indications are discussed in the IB.

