### 8.3.6 Adverse event of special interest

#### Adverse event of special interest

An adverse event of special interest (AESI) is an AE (serious or nonserious) of scientific and medical concern specific to the Sponsor's product or program, for which ongoing monitoring and immediate notification by the Investigator to the Sponsor is required. Such events may require further investigation in order to characterize and understand them. Adverse events of special interest may be added, modified, or removed during a study by protocol amendment.

For these AESIs, the Sponsor will be informed immediately (ie, within 24 hours), per SAE notification described in [Section 10.3](#), even if not fulfilling a seriousness criterion, using the corresponding pages in the eCRF (to be sent) or screens in the eCRF. Adverse event of special interests for this study include:

- Anaphylactic reactions.
- Systemic hypersensitivity reactions.
- Helminthic infections.
- Any severe type of conjunctivitis or blepharitis.
- Keratitis.
- Clinically symptomatic eosinophilia (or eosinophilia associated with clinical symptoms).
- Pregnancy of a female participant entered in a study as well as pregnancy occurring in a female partner of a male participant entered in the study with IMP:
  - Pregnancy occurring in a female participant entered in the clinical trial or in a female partner of a male participant entered in the clinical trial will be qualified as an SAE only if it fulfills one of the seriousness criteria,
  - In the event of pregnancy in a female participant, IMP should be discontinued,
  - Follow-up of the pregnancy in a female participant or in a female partner of a male participant is mandatory until the outcome has been determined,
  - Abnormal pregnancy outcomes (eg, spontaneous abortion, fetal death, stillbirth, congenital anomalies, ectopic pregnancy) are considered SAEs.

- Significant ALT elevation:
  - ALT  $>5 \times$  ULN in participants with baseline ALT  $\leq 2 \times$  ULN,
  - OR
  - ALT  $>8 \times$  ULN if baseline ALT  $>2 \times$  ULN.
- Symptomatic overdose (serious or nonserious) with IMP/NIMP

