#### **Events meeting the AE definition**

- Any abnormal laboratory test results (hematology, clinical chemistry, or urinalysis) or other safety assessments (eg, ECG, radiological scans, vital signs measurements), including those that worsen from baseline, considered clinically significant in the medical and scientific judgment of the Investigator (ie, not related to progression of underlying disease).
- Exacerbation of a chronic or intermittent pre-existing condition including either an increase in frequency and/or intensity of the condition.
- New conditions detected or diagnosed after study intervention administration even though it may have been present before the start of the study.
- Signs, symptoms, or the clinical sequelae of a suspected drug-drug interaction.
- Signs, symptoms, or the clinical sequelae of a suspected overdose of either study intervention or a concomitant medication.
- "Lack of efficacy" or "failure of expected pharmacological action" per se will not be reported as an AE or SAE. Such instances will be captured in the efficacy assessments. However, the signs, symptoms, and/or clinical sequelae resulting from lack of efficacy will be reported as AE or SAE if they fulfill the definition of an AE or SAE.

The signs, symptoms, and/or clinical sequelae resulting from lack of efficacy will be reported as AE or SAE if they fulfil the definition of an AE or SAE. Also, "lack of efficacy" or "failure of expected pharmacological action" also constitutes an AE or SAE.

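### The AESI row labelled clinically symptomatic eosinophilia counts all eosinophilia adverse events, and no planned table gives the medically reviewed symptomatic count by arm

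*SAP*

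**What the plan says.** Protocol section 8.3.6 lists among the AESIs "Clinically symptomatic eosinophilia (or eosinophilia associated with clinical symptoms" (closing bracket cut). Symptoms are part of the definition. Section 2.3.1 names the important potential risk as "eosinophilia associated with clinical symptoms in asthma patients" and says of the laboratory finding: "The observed increase in eosinophil count is transient, which is consistent with the current understanding of the mechanism of action of dupilumab".

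SAP section 3.6.2, Table 6, has an AESI row with the protocol's label. Its criteria cell uses CMQ10641 and reads, in part, "Eosinophilic disorders or PT = Eosinophil count increased followed by blinded medical review". Footnote b, attached to the row label, reads "All cases of Eosinophilia will be included in the analysis, where cases associated with clinical symptoms will be further described in the CSR".

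Table 6 defines what is analysed as an AESI, so this row feeds:

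- the overview line "Any treatment-emergent AESI";
- the summaries planned for every AESI (seriousness, death, discontinuation, relatedness, intensity, outcome and an exposure-adjusted figure);
- the further rates per 100 participant-years, if cumulative exposure turns out imbalanced between the arms.

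The SAP also plans a separate summary of the AESIs that investigators report in the eCRF, and shows events of interest by preferred term where applicable.

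**The concern.** The label and the counted set differ. A reader of the safety tables will take the row as the incidence of symptomatic eosinophilia, because that is its title and the protocol's definition. Under footnote b it is the incidence of any eosinophilia adverse event found by the search. The symptomatic subset, which is the event the protocol singled out, appears only as description in the study report.

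Two things are at stake. The incidence shown for this AESI can be above zero when no participant had the event as defined, and the aggregate AESI line takes on the same excess. And no planned table compares the arms on symptomatic cases confirmed by medical review, although a review of these cases is already planned.

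**Working it through.** The documents give no figure for this point, so there is none to reproduce. The check is a comparison of texts, followed by an illustration of size.

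**1. What enters the row.** Table 6 selects coded adverse events, not laboratory values. Under protocol section 10.3.1 an abnormal laboratory result is an adverse event when "considered clinically significant in the medical and scientific judgment of the Investigator". A transient rise that the investigator does not judge clinically significant therefore stays out. A symptom-free rise that is so judged, and is recorded, can code to the count-increased term and enter.

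**2. What the blinded review does.** Three AESI rows that use a broad search add such a review:

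| Row | Stated purpose of the review |
|---|---|
| Anaphylactic reaction | Decides whether cases found by the algorithm are anaphylaxis |
| Systemic hypersensitivity | "followed by blinded medical review (documented process) for selection of relevant systemic hypersensitivity events" |
| Symptomatic eosinophilia | None stated |

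**3. Whether label, cell and footnote can all hold.** Take the possible purposes of the eosinophilia review in turn.

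- It removes symptom-free cases: the label is right, but footnote b, which includes all cases, is wrong.
- It only marks which cases the study report will describe: footnote b is right, but the label is wrong.
- It confirms that a coded event is eosinophilia at all, regardless of symptoms: footnote b is right for confirmed cases, but the label is still wrong.

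None of these readings makes the label and the footnote both true. Footnote b is the only explicit statement of what is counted, so following it puts symptom-free events in the row.

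**4. Whether another planned output supplies the missing count.** The investigator-reported summary follows the investigator's own AESI classification, not the medical review. The split by preferred term separates the term for a raised count from other terms, but that term does not say whether symptoms were present. Neither is a reviewed symptomatic count by arm.

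**5. Size.** Inputs: n = 35 per arm (protocol section 4.1, approximate). The rate p of participants with a symptom-free eosinophilia adverse event is assumed, because the documents give none for either arm. Participants are taken as independent.

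- Contribution of one participant: 1/35 = 2.9 percentage points.
- Expected number in an arm: 35 × p.
- Chance of at least one: 1 − (1 − p)^35.

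| Assumed p | Expected number | Chance of at least one |
|---|---|---|
| 1% | 0.35 | 29.7% |
| 2% | 0.70 | 50.7% |
| 5% | 1.75 | 83.4% |
| 10% | 3.50 | 97.5% |

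Under footnote b each of these participants counts in the row. Under the definition in protocol section 8.3.6 none does.

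**The case against.** The case for leaving the plan alone has several parts.

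- *Broad capture is a defensible safety convention.* The rule is prespecified and disclosed in the same table, it hides no symptomatic case, and it errs by over-counting. This stands as an argument for showing the broad count. It does not support giving that count the narrow label.
- *The gap is partly filled.* Investigators are asked to report only symptomatic eosinophilia as this AESI, and their reports are tabulated separately. With about 35 per arm, a reader could probably count symptomatic cases from the study report. This softens the point, but it still yields no reviewed count by arm in a planned table.
- *The consequence is limited.* The safety analysis is descriptive, no hypothesis is tested and no decision rule uses this count. This stands and limits the severity.
- *The review's role is ambiguous.* The cell may have been meant as a filter. That is fair: the text does not settle the intent. It shows that the cell and the footnote need reconciling.

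Some stronger readings are tempting, and the documents do not support them.

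- A reader might infer that every count rise expected from dupilumab will be reported as the AESI. Only rises that become adverse events can enter.
- A reader might infer that the excess must fall mainly on the dupilumab arm, since section 2.3.1 lists eosinophilia as an adverse drug reaction. The same section says those reactions were not seen consistently in all indications, and neither document gives a rate by arm in this disease.
- A reader might infer that the row reports the protocol's named potential risk. That risk is specific to patients with asthma, while up to 70% of participants may have none and the row covers everyone.

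**Conclusion.** The mismatch is real on the current text. The row and the protocol define symptomatic eosinophilia, footnote b counts all eosinophilia adverse events, and the review that could separate them has no stated purpose. The count carries into the overview AESI line, the per-AESI summaries and any exposure-adjusted AESI rates.

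The size is known only per case: 2.9 percentage points for each symptom-free participant at 35 per arm. Whether any occur depends on an event rate that the documents do not give. Over assumed rates of 1% to 10%, the chance of at least one in an arm is about 30% to 97.5%. These figures apply to either arm and say nothing about a difference between arms.

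Severity is minor to moderate: a labelling and counting error in a descriptive safety table, with no bearing on efficacy.

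**What to change.** In SAP Table 6:

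1. State that the blinded medical review determines whether each eosinophilia case was clinically symptomatic.
2. Under the AESI label, count only cases confirmed as symptomatic, and use these in the overview AESI line, the per-AESI summaries and any exposure-adjusted AESI rates.
3. Under the other selected AE groupings, add a row for eosinophilia (all cases) from the full CMQ10641 search.
4. Reword footnote b to match.

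The SAP already handles conjunctivitis this way, with a severe-only AESI and broader groupings listed separately. The cost is SAP wording and one extra table row. The review is already planned, no new data are collected, and the broad count is kept. The change should be made before unblinding.
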